7.1 Sample Size Determination

The planned sample size is 20 patients in each arm, for a total of 40 study patients. Assuming a dropout rate of 20%, the goal is to enroll 50 patients. The estimated baseline mean eosinophil count is expected to be between 80-110 eos/hpf, with an estimated standard deviation of change from baseline in eosinophil counts of 30-50 eos/hpf. Using a conservative standard deviation assumption of 50 eos/hpf, a sample size of 25 patients in each arm provides 80% power to detect a significant between group difference of 40%. Using a conservative standard deviation assumption of 50 eos/hpf, a sample size of 16 patients in each arm provides 80% power to detect a significant between group difference of 50%.

Pilot studies evaluating other medications in EoE have used similar sample sizes. [15, 16]

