3.2 Number of Subjects

The planned sample size is 20 patients in each arm, for a total of 40 study patients. Assuming a dropout rate of 20%, the goal is to enroll 50 patients. The estimated baseline mean eosinophil count is expected to be between 80-110 eos/hpf, with an estimated standard deviation of change from baseline in eosinophil counts of 30-50 eos/hpf. Using a conservative standard deviation assumption of 50 eos/hpf, a sample size of 25 patients in each arm provides 80% power to detect a significant between group difference of 40%. Using a conservative standard deviation assumption of 50 eos/hpf, a sample size of 16 patients in each arm provides 80% power to detect a significant between group difference of 50%.

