4.4 Early Withdrawal of Subjects

4.4.1 When and How to Withdraw Subjects

Subjects may be withdrawn from the study for safety issues, failure of subject to adhere to protocol requirements, and subject decision to withdraw from the study. Safety issues include adverse effects from the study drugs, or inability to tolerate the study drugs. Failure of subjects to adhere to protocol requirements includes adherence to the medication regimen, absence of follow-up visits, or not completing study questionnaires. As there is a 6 week wash out period prior to study inclusion, patients may have worsening of symptoms of EoE while off prior medications. Patients who have worsening or relapse of symptoms of EoE while enrolled in the trial will be removed from the study.

For patients who do not tolerate the study drug, other treatment alternatives will be offered, including PPIs, corticosteroids, and/or diet modification.

Data will be collected on withdrawn subjects up until the point of study withdrawal. A scheduled follow-up appointment will be ordered in clinic following study withdrawal.

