4.4.2 Data Collection and Follow-up for Withdrawn Subjects

A follow-up appointment will be ordered at the 12 week period after initiation of the study drug or placebo.

5 Study Drug

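### The 80% power quoted for a 40% difference is for the 25 per arm enrolled; the 20 per arm left after the plan's own 20% dropout give about 69% (51–77% over its baseline range) at its SD of 50

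*Combined protocol and SAP*

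**What the plan says.** Sections 3.2 and 7.1 carry the same sample size text. The target is given first: "The planned sample size is 20 patients in each arm, for a total of 40 study patients". Enrolment is then raised for losses: "Assuming a dropout rate of 20%, the goal is to enroll 50 patients". With 1:1 allocation that is 25 per arm enrolled.

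The assumption for the starting level is: "The estimated baseline mean eosinophil count is expected to be between 80-110 eos/hpf". For variability, the plan works "with an estimated standard deviation of change from baseline in eosinophil counts of 30-50 eos/hpf". The upper end, 50 eos/hpf, is adopted as the conservative value. Two power statements follow, both at that SD:

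- "a sample size of 25 patients in each arm provides 80% power to detect a significant between group difference of 40" percent;
- "a sample size of 16 patients in each arm provides 80% power to detect a significant between group difference of 50" percent.

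Neither is for 20 per arm, and neither says what the percentage is a percentage of.

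On losses, section 4.4.1 says "Data will be collected on withdrawn subjects up until the point of study withdrawal". Section 4.4.2 says "A follow-up appointment will be ordered at the 12 week period after initiation of the study drug or placebo", without mentioning endoscopy or biopsy. Section 7.2 deals with missing data only by data queries. Section 7.3 lists four analysis populations and does not name one as primary.

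**The concern.** The same five patients per arm are used twice: once as the allowance for dropout, and once in the sample size that gives 80% power for the 40% difference. If dropout is as the plan expects, those five will not supply a week-12 eosinophil count, and the 40% statement describes a larger trial than the one to be analysed.

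This matters most if the result is null. Sections 3.2 and 7.1 are the only place where a reader can learn what difference the trial could have missed. They suggest that 40% was covered with 80% power at a conservative SD, and give no figure for the number the plan expects to analyse.

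**Working it through.** **Inputs.** Two-sided alpha 0.05 and a two-sample t-test (or rank sum test) between arms, from 7.2; 1:1 allocation, from 5.7; SD of change 30–50 with 50 adopted, baseline mean 80–110, 20 per arm planned, 20% dropout and 50 enrolled, from 3.2 and 7.1.

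**Step 1: dropout inflation.** 20 / (1 − 0.20) = 25 per arm, or 50 in total. This is correct, and it shows that 25 is the enrolled number and 20 the number expected to remain.

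**Step 2: reproduce the plan's figures.** Normal approximation, per arm: n = 2 × (1.96 + 0.8416)² × (SD/δ)².

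- δ = 40, SD 50: 2 × 7.849 × 1.5625 = 24.5, rounded up to 25.
- δ = 50, SD 50: 2 × 7.849 × 1 = 15.7, rounded up to 16.

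Both quoted sizes therefore follow if 40% and 50% mean 40 and 50 eos/hpf, that is, a baseline mean of 100. The reading is tight: rounding up to 25 for 40% needs a baseline of 99.1–101.1, and rounding up to 16 for 50% needs 99.1–102.3. At 25 per arm and δ = 40, power is 80.7% by the normal approximation and 79.1% by the exact (noncentral) t-test. The plan's statement holds on this reading.

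**Step 3: power at 20 per arm.** The noncentrality is δ / (SD × √(2/n)). For δ = 40, SD 50 and n = 20 it is 40 / (50 × 0.3162) = 2.530. With 38 degrees of freedom (critical value 2.024), exact power is 69.3%. The normal approximation gives 71.6%. Like for like, going from 25 to 20 per arm lowers power from 79.1% to 69.3% (t-test) or from 80.7% to 71.6% (normal).

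**Step 4: over the plan's own ranges.** Exact t-test, two-sided 0.05; percentages taken of the baseline mean:

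| Scenario | Baseline 80 | 90 | 100 | 110 |
|---|---|---|---|---|
| 40%, 20 per arm, SD 50 | 50.5% | 60.2% | 69.3% | 77.4% |
| 40%, 20 per arm, SD 40 | 69.3% | 79.2% | 86.9% | 92.4% |
| 40%, 20 per arm, SD 30 | 90.8% | 95.9% | 98.4% | 99.5% |
| 50%, 20 per arm, SD 50 | 69.3% | 79.2% | 86.9% | 92.4% |
| 40%, 25 per arm, SD 50 | 60.2% | 70.3% | 79.1% | 86.2% |

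By the normal approximation the first row runs from 52.6% to 79.5%, also below 80% throughout.

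**Step 5: what 20 per arm can detect.** At SD 50 the difference with 80% power is 45.5 eos/hpf: 45.5/110 = 41%, 45.5/100 = 45% and 45.5/80 = 57% of baseline. It scales with the SD: 36.4 at SD 40 and 27.3 at SD 30. Conversely, 20 per arm reach 80% power for a 40% difference only if the SD is no more than 35.2, 39.6, 44.0 or 48.4 at baselines 80, 90, 100 or 110.

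**The case against.** The strongest reply is that no stated number is wrong. Both conditional statements reproduce, the dropout inflation is right, and the plan never claims 80% power for 40% with 20 per arm. The planned 20 lies between 16 and 25, so a reader could place the detectable difference between 40% and 50%, and the 45% found here lies inside that bracket. SD 50 is the top of the plan's range; at SD 40 and baseline 100, power is 87%. This is a small single-site phase II trial whose size is also supported by reference to similar pilot studies.

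Much of this stands. The defect lies in which sample size the power is attached to, not in a miscalculation, and it is confined mainly to the 40% scenario at the high SD. It does not remove the point. Interpolating between 16 and 25 requires a baseline of about 100, which the plan does not state; at baseline 80, even the 50% difference has only 69% power. The plan chose SD 50 as its conservative case and made its power statements there, so that is where they should hold for the number it expects to analyse.

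One could also argue that dropouts will be analysed, keeping 25 per arm. That 20 will be evaluable is indeed an inference. But the plan describes no route by which a withdrawn patient supplies a week-12 count: data stop at withdrawal, the later appointment mentions no biopsy, and no imputation is specified.

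**Conclusion.** The concern holds. At the SD the plan adopted, the 20 per arm it expects after dropout have 69% power for a 40% difference at the implied baseline of 100, and less than 80% at every baseline in its range (51% to 77%). The plan states no power for that number. The 50% scenario is met at baseline 100 (87%) but not at 80 (69%) and only nearly at 90 (79%).

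The conclusion rests on three assumptions: the percentages refer to the baseline mean, as the reproduced sample sizes indicate; dropouts contribute no week-12 count; and the test is a two-sided two-sample t-test on change from baseline. If the SD is nearer 40 and the baseline about 100 or higher, the 40% difference is adequately powered. The design is not invalidated, but the power statement should be corrected.

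**What to change.** In 3.2 and 7.1, add the sentence below, and either remove the 25-per-arm statement or label it as assuming no dropout and a baseline mean of 100:

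> With 20 evaluable patients per arm, an SD of change of 50 eos/hpf and a two-sided two-sample t-test at 0.05, the trial has 80% power for a between-arm difference in change from baseline of 45.5 eos/hpf (41% of a baseline mean of 110, 45% of 100, 57% of 80). Power is 69% for a difference of 40 eos/hpf and 87% for 50 eos/hpf.

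This figure applies to a between-arm comparison of change. Section 7.2 compares counts between arms at baseline and at 12 weeks, and mentions change only within the treatment arm. It should name the between-arm test that the figure powers. The plan gives no SD for week-12 counts, so the power of a comparison of those counts cannot be worked out from it.

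The cost is wording in 3.2 and 7.1 and one clause in 7.2. No patients are added; the stated power becomes less favourable.

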7.2 Statistical Methods

Descriptive Statistics

Means and standard deviations will be used to summarize quantitative and continuous variables. These will include age, dysphagia questionnaire scores, and eosinophils per hpf on histology. Frequencies and percentages will be used to summarize categorical variables including gender; the proportion of patients that have symptomatic and histologic improvement in symptoms on placebo; and the proportion of patients that have symptomatic and histologic improvement in symptoms on anti-histamines.

Handling of Missing Data

We will perform data queries for missing dysphagia questionnaires and pathology reports.

Primary Hypothesis: Antihistamines are effective for the treatment of EoE and will result in symptomatic improvement as assessed by patient questionnaires and endoscopic and histologic improvement as assessed by endoscopic score and by eosinophil counts on biopsy.

Continuous demographic variables, peak eosinophil counts and dysphagia and GERD questionnaire scores at baseline and 12 weeks will be compared between the treatment and placebo arms using a two-sample t test or Wilcoxon rank sum test where appropriate. Categorical demographic variable and percentage of patients with histologic response of ≤15 eos/hpf at 12 weeks will be compared between the two arms using Chi-squared test or Fisher's exact test. The changes in peak counts and questionnaire scores in the treatment arm from baseline to 12 weeks will be compared suing a paired t-test or signed rank test

All tests will be two-sided with alpha level set at 0.05 for statistical significance.

Interim Analysis

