4.1 Inclusion Criteria

- 1. Patients over the age of 18, male and female.
- 2. Patients who carry the diagnosis of EoE based on esophageal biopsies obtained within 6 months prior to enrollment (>15 eosinophils per hpf on at least 2 esophageal levels)
- 3. Subjects must be able to give appropriate informed consent

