6.4 Visit 4 (12 week follow-up)

At the 12 week follow-up visit with a physician, we will review the results of the DSQ to be completed for weeks 10-12 of the study drugs. The 12 week follow-up appointment will occur no earlier than 12 weeks after initiation of the study drug and no later than 14 weeks after initiation. The patient will meet with one of the study investigators, and be consented for an EGD. An EGD with esophageal biopsies will be performed. Prior to EGD, a complete blood count and basic

metabolic panel will be ordered as routine per institutional policy. Either KD or DF will perform the EGD in the endoscopy suite, per our institution's standard protocol. Any macroscopic abnormalities seen in the esophagus will be documented and photographed. Any lesions in the upper digestive tract seen on EGD will be biopsied and treated as deemed appropriate by the performing endoscopist. Biopsy specimens will be labeled and placed in a container and labeled with the patient's ID number.

The eosinophil count will be determined by the study pathologist for the post-treatment exam using a previously validated protocol. [2, 3] Four esophageal biopsies will be sampled from both the distal esophagus (3cm above the GE junction) and proximal esophagus (at least 10 cm above the GE junction) to maximize sensitivity of detecting eosinophils.[1] On each biopsy fragment, 5 high-power fields will be examined and the overall peak eosinophil count determined from the field deemed to be most inflamed from all esophageal levels and all high power fields. [4]

Symptomatic improvement will be defined as at least 2 levels on the dysphagia questionnaire.

Study Activity	Week 0 (initial enrollment appointment)	Week 6	Week 10	Weeks 14-16 (follow-up appointment)
Study Agent(s) (weeks 2-14)		X	X	
Informed consent	X			
Physician office visit with medication review and physical exam	X			X
Phone or office visit with study coordinator		X	X	
Pill count		X	X	X
Drug diary		X	X	
Adverse event evaluation		X	X	Х

B-HCG (non-menopausal females)	X		
Dysphagia Symptom Questionnaire (complete weeks 0-2 and 12-14)	X		X
CBC and BMP			X
EGD w/ biopsy			X

7 Statistical Plan

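### No between-arm analysis in 7.2 adjusts for baseline peak eosinophil count or baseline DSQ, although the trial is sized on change from baseline; adjustment costs almost nothing and may recover useful power

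*Combined protocol and SAP*

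**What the plan says.** - **Between arms (7.2 Statistical Methods).** "peak eosinophil counts and dysphagia and GERD questionnaire scores at baseline and 12 weeks will be compared between the treatment and placebo arms". The listed tests are the two-sample t and the Wilcoxon rank sum, whichever is appropriate. No regression, ANCOVA or baseline covariate is named anywhere in the document.
- **Within the treatment arm (Study Summary and 7.2).** Change from baseline to 12 weeks in peak count and questionnaire scores is tested by paired t or signed rank test. No between-arm test of change is listed.
- **Sample size (7.1, repeated in 3.2).** The calculation rests on an "estimated standard deviation of change from baseline in eosinophil counts of 30-50 eos/hpf" and takes 50 as the conservative value. The plan is 20 evaluable patients per arm.
- **Baseline DSQ (3.1, 6.1 and the schedule in 6.4).** It is completed daily for two weeks before study drug starts: "Dysphagia Symptom Questionnaire (complete weeks 0-2 and 12-14".
- **Baseline peak count (4.1 Inclusion Criteria).** The diagnosis rests on "biopsies obtained within 6 months prior to enrollment". The schedule table in 6.4 shows endoscopy with biopsy at the final visit only.
- **Error rate (7.2).** "All tests will be two-sided with alpha level set at 0.05 for statistical significance".

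**The concern.** The comparison that answers the trial's question is active against placebo at week 12, and in this plan it ignores each patient's starting value. Two things follow. Variance in the week-12 value that baseline could explain stays in the error term. And a chance baseline imbalance, which is likely to be visible with about 20 per arm (the baseline mean difference has a standard error of √(2/20) = 0.32 SD), passes into the estimate in proportion to r.

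The between-arm test at baseline remedies neither. Under randomisation any baseline difference is due to chance, so the test has nothing to detect, and its result is not carried into the week-12 analysis. The paired test uses baseline but cannot separate drug effect from regression to the mean or natural course.

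There is also a mismatch inside the plan. Section 7.1 uses the SD of change, while the between-arm test in 7.2 is of week-12 values. With equal variances at the two times, those SDs agree only when r = 0.5.

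**Working it through.** **1. The plan's own sample sizes.** Inputs from 7.1 and 7.2: SD 50, two-sided 0.05, 80% power. The effects are percentages of a baseline mean given as a range ("The estimated baseline mean eosinophil count is expected to be between 80-110 eos/hpf"). I assume a mean of 100, so 40% and 50% become 40 and 50 eos/hpf. With n per arm = 2(1.960 + 0.842)² × SD²/δ²:
- δ = 40: 2 × 7.85 × 2500/1600 = 24.5, so 25.
- δ = 50: 2 × 7.85 × 2500/2500 = 15.7, so 16.
- Dropout: 40/0.8 = 50 enrolled.

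All three match 7.1. At baseline means of 80 and 110 the figures become 39 and 25, and 21 and 13, so 100 appears to be the value used.

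**2. SD of each between-arm analysis.** Let r be the correlation between baseline and week 12. The documents do not give it, so a range is used. Assume equal variances at the two times and SD of change = 50.
- Week-12 value: 50/√(2(1 − r)).
- ANCOVA residual: the week-12 SD × √(1 − r²) = 50√((1 + r)/2).
- Change score: 50 at every r.

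**3. Power at 20 per arm, δ = 40 eos/hpf.** Noncentral t with noncentrality δ/(SD × √(2/20)), two-sided 0.05, 38 df (37 for ANCOVA). At r = 0.5, the week-12 test has 40/(50 × 0.316) = 2.53, giving 69%. ANCOVA has 40/(43.30 × 0.316) = 2.92, giving 81%.

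| r | Week-12 SD | ANCOVA SD | Week-12 t-test | ANCOVA |
|---|---|---|---|---|
| 0 | 35.4 | 35.4 | 94% | 94% |
| 0.2 | 39.5 | 38.7 | 88% | 89% |
| 0.3 | 42.3 | 40.3 | 83% | 86% |
| 0.5 | 50.0 | 43.3 | 69% | 81% |
| 0.6 | 55.9 | 44.7 | 60% | 79% |

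A between-arm change-score test, which the plan does not list, has 69% at every r. At r = 0.5 the 95% CI half-width falls from 32 to 28 eos/hpf. Allowing for random baseline imbalance (variance factor about 1 + 1/36) takes about one point off ANCOVA power: 88%, 85%, 80% and 78% at r = 0.2, 0.3, 0.5 and 0.6.

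**4. Sensitivity to the inputs.**
- SD of change 40 or 30, r = 0.5: the week-12 test already has 87% or 98%, against 94% or over 99% for ANCOVA.
- δ = 32 or 44 (40% of 80 or 110), SD 50, r = 0.5: 51% vs 62%, or 77% vs 88%.
- Week-12 SD fixed at 50 instead of the SD of change: the week-12 test has 69% at every r. ANCOVA has 68% to 69% at r = 0 and 80% to 81% at r = 0.5, the lower figures allowing for imbalance.

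**5. Skewed counts.** The plan allows Wilcoxon, so the t-test is not the only comparator. In a simulation with lognormal counts, mean 100, an assumed coefficient of variation of 1.0, a 40% multiplicative effect, 20 per arm and r = 0.2, power was 45% for Wilcoxon, 35% for raw-scale ANCOVA, 46% for log-scale ANCOVA and 45% for rank ANCOVA. Log and rank ANCOVA stayed within about one point of Wilcoxon at low r and beat it from r = 0.3.

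**The case against.** The strongest reply is that the plan's test is valid. Randomisation protects the unadjusted comparison, and a baseline test between arms, though uninformative, does not harm the week-12 result. That stands.

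Second, r may well be low for the primary endpoint. The qualifying biopsy can be up to 6 months old at enrolment, while the medication exclusions in 4.2 look back only 6 weeks, so it may predate washout. Section 6.4 describes the study pathologist's count for the post-treatment examination only. At r = 0.2 the gain is about one point, and after allowing for baseline imbalance it is close to nil. This also stands, but only for histology. The DSQ baseline is collected in the trial just before treatment.

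Third, SD 50 is the pessimistic end of the stated range, and at 30 or 40 power is already high. That is correct for the peak count. It limits the size of the point and does not remove it.

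A reader might infer that baseline is used for nothing but a significance test. The documents do not support that: it also enters the paired treatment-arm test, and the symptom-response definition in 6.4 reads as a change. A reader might also infer that ordinary raw-scale ANCOVA can only help. Against the plan's Wilcoxon option, with skewed counts and a weak baseline, it can lose about ten points, so the scale matters.

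**Conclusion.** The point holds as one of efficiency. No between-arm estimate uses baseline, although the sample size is framed in terms of change from baseline. Under SD of change 50, equal variances, a 40 eos/hpf difference and 20 per arm, the gain from ANCOVA over the week-12 t-test runs from nothing at r = 0, through 1 point at r = 0.2 and 3 at r = 0.3, to 12 at r = 0.5 and 19 at r = 0.6. The correlation, the 40 eos/hpf and the equal variances are assumptions; the SD is the upper end of the plan's range. The residual variance factor against the week-12 test, 1 − r², applies equally to DSQ, where the case is strongest.

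A reader might infer that the planned test is biased, or that the trial is sure to lose ten or more points of power. Neither follows: the test is valid, and the loss depends on a correlation that the documents do not give. What supports the change is the asymmetry. With a suitable scale, a useless baseline costs about a point of power, while a moderately predictive one returns much more.

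**What to change.** In 7.2:
1. **Week-12 DSQ:** ANCOVA on arm and baseline DSQ, reporting the adjusted difference with its 95% CI.
2. **Week-12 peak count:** ANCOVA on arm and baseline peak count on a log scale, for example log(count + 1), or on a rank scale. Choose one in advance. Report the adjusted ratio with its 95% CI if the log scale is used. Keep the unadjusted Wilcoxon test as sensitivity analysis.
3. **Baseline definition:** state that the peak count from the qualifying biopsy is the baseline value.
4. **Baseline table:** show baseline variables descriptively and delete the between-arm significance tests of them.

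The cost is SAP wording, settled before any unblinded analysis, and one degree of freedom per model. On the log scale the effect is a ratio, not a difference in eos/hpf; a rank analysis gives no direct estimate on the count scale. No visit, procedure or patient is added. One practical condition is that a numeric peak must be available for every qualifying biopsy, including those found in outside records, so this should be confirmed when the baseline is defined.

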Objectives	To assess the efficacy of antihistamines in the treatment of eosinophilic esophagitis. Primary outcomes are the number of eosinophils on histology and safety. Secondary outcomes are changes in dysphagia symptom questionnaire score, EoE endoscopic reference score, and the percentage of patients with histologic response of ≤15 eos/hpf on biopsy.			
Number of Subjects	The planned sample size is 20 patients in each arm, for a total of 40 study patients. Assuming a dropout rate of 20%, the goal is to enroll 50 patients.			
Diagnosis and Main Inclusion Criteria	Consentable, nonpregnant adults with a diagnosis of eosinophilic esophagitis			
Study Product, Dose, Route, Regimen	Famotidine 40 mg tab twice daily by mouth and loratadine 10 mg tab once daily by mouth for 12 week duration.			
Duration of Administration	12 weeks			
Reference therapy	Placebo			
Statistical Methodology	Patients will be randomized in a 1:1 fashion by a computer generated program. The changes in peak counts and questionnaire scores in the treatment arm from baseline to 12 weeks will be compared using a paired t-test or signed rank test. Categorical demographic variables and percentage of patients with histologic response of ≤15 eos/hpf at 12 weeks will be compared between the two arms using Chi-squared test or Fisher's exact test.			

1 Introduction

This document is a protocol for a human research study. This study will be carried out in accordance with the applicable United States government regulations and Mayo Clinic research policies and procedures.

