3.4 Primary Study Endpoints

To determine whether loratedine and famotidine are effective for improving maximum eosinophil counts (eos/hpf) after 12 weeks of therapy with antihistamines in patients with EoE. To assess the safety and tolerability of H1 and H2 antihistamines in subjects with EoE.

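### No primary test is named for peak eosinophil count: the between-arm week-12 test is unadjusted, and change is tested only within the treated arm

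*Combined protocol and SAP*

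**What the plan says.** Section 3.4 sets the primary efficacy question as whether the drugs are "effective for improving maximum eosinophil counts (eos/hpf) after 12 weeks of therapy with antihistamines in patients with EoE". It does not say whether the variable is the week-12 count or the change from baseline.

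Section 7.2 gives two analyses of that count:

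- Between arms: counts at baseline and at 12 weeks "will be compared between the treatment and placebo arms using a two-sample t test or Wilcoxon rank sum test where appropriate". No covariate is included.
- Within the treated arm: "The changes in peak counts and questionnaire scores in the treatment arm from baseline to 12 weeks will be compared suing a paired t-test". A rank-based alternative is allowed.

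Neither is labelled primary. The primary hypothesis in 7.2 covers symptoms, endoscopic score and histology together, so it does not choose between them. The Study Summary (Statistical Methodology) carries only the second for the count: "The changes in peak counts and questionnaire scores in the treatment arm from baseline to 12 weeks will be compared using a paired t-test", with the same rank-based alternative. Its one between-arm efficacy test is the percentage at or below 15 eos/hpf, which the Summary lists as a secondary outcome.

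Section 7.1 sizes the trial for a between-group difference, "with an estimated standard deviation of change from baseline in eosinophil counts of 30-50 eos/hpf". Section 7.2 contains no between-arm test of change and no baseline-adjusted between-arm test.

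**The concern.** The Study Summary, 7.1 and 7.2 point to different analyses of the same variable. The Summary tests the treated arm against itself. The sample size assumes a between-arm comparison of change. Section 7.2 offers a between-arm comparison of week-12 counts and also repeats the Summary's test.

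A before-and-after test in one arm makes no use of the placebo group. Any movement that both arms share is counted as treatment effect, and there are reasons in the protocol to expect some. Section 4.1 takes the baseline from "Patients who carry the diagnosis of EoE based on esophageal biopsies obtained within 6 months prior to enrollment", selected for a high count. Section 6.4 assigns the study pathologist to the post-treatment reading only. Patients must have been off several drug classes for 6 weeks, and 4.4.1 warns that "patients may have worsening of symptoms of EoE while off prior medications". The documents give neither the size nor the direction of the net shift.

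At stake are two things. With no primary test named, an uncontrolled result could be reported as the answer of a placebo-controlled trial. And the between-arm test that is planned leaves the baseline count unused, which costs power if baseline and week 12 are at least moderately correlated.

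**Working it through.** **Inputs from the documents.** Two-sided alpha 0.05 (7.2). SD of change 30 to 50 eos/hpf, baseline mean 80 to 110, 20 evaluable patients per arm, 50 enrolled (7.1). **Assumptions, not in the documents:** a shared mean change m in both arms; the correlation r between baseline and week-12 counts; equal SDs at the two times; normal data on the raw count scale.

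**1. The plan's own figures.** n per arm = 2 × (1.960 + 0.842)² × SD² / difference². With SD 50 and a difference of 40 (40% of an inferred baseline of 100): 2 × 7.85 × 2500 / 1600 = 24.5, so 25. With a difference of 50: 15.7, so 16. Both match 7.1. The sizing is therefore a two-sample comparison of change, which 7.2 does not list.

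**2. The treated-arm paired test when the drug does nothing.** Noncentral t with 19 df and noncentrality m / (SD/√20). For m = 10 and SD 50 the noncentrality is 10 / 11.18 = 0.89; for SD 30 it is 10 / 6.71 = 1.49. Chance of a significant result:

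| Shared fall (eos/hpf) | SD of change 50 | SD of change 30 |
|---|---|---|
| 5 | 7% | 11% |
| 10 | 14% | 29% |
| 20 | 40% | 81% |

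The between-arm week-12 test stays at about 5%, because the shared change cancels.

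**3. Two tests, neither named.** Simulation of 40,000 trials per case, 20 per arm, r = 0.3, 0.5 and 0.7, no drug effect, counting significance in either direction. With no shared change, at least one test is significant in about 9.4%. With a shared fall of 10, the figure is 17% to 18% (SD 50) or 32% to 33% (SD 30).

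**4. Power of the between-arm test with and without baseline.** Week-12 SD: s = SD of change / √(2(1 − r)). ANCOVA residual SD: s × √(1 − r²). Noncentral t with 38 df (unadjusted) and 37 df (ANCOVA), 20 per arm, difference 40. Example at r = 0.5 and SD of change 50: s = 50, ANCOVA SD = 50 × 0.866 = 43.3.

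| SD of change | r | Unadjusted | ANCOVA |
|---|---|---|---|
| 50 | 0 | 94% | 94% |
| 50 | 0.2 | 88% | 89% |
| 50 | 0.3 | 83% | 86% |
| 50 | 0.5 | 69% | 81% |
| 50 | 0.7 | 48% | 76% |
| 30 | 0.5 | 98% | above 99% |
| 30 | 0.7 | 89% | 99% |

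The unadjusted week-12 test has the same SD as the one used in 7.1 only at r = 0.5.

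**The case against.** The trial is randomised and placebo-controlled, it is sized on a between-group difference, and 7.2 lists the between-arm comparison before the paired test. A fair reader would take the between-arm test as the main one, and it is valid. The Summary is an abbreviated table, and its responder comparison is a between-arm test of a dichotomised count. On this view the defect is a missing label. That a valid test is planned is true and limits the severity. But the label is missing, and the only test of the count itself in the Summary is the uncontrolled one.

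The error rates can also be called selective. The 9.4% counts significant worsening; results that favour the drug make up about 4.7%, against 2.5% for one named test. If the shared change were a rise of 10, the paired test would falsely favour the drug in under 0.3% of trials. Regression to the mean from the entry threshold alone, under a normal model with r 0.3 to 0.7 and SD of change 50, gives a fall of only about 1 to 6 eos/hpf. These points stand: the 40% and 81% figures rest on a fall of 20 that nothing in the documents supports. They show that the size is unknown; they do not make the paired test a comparison with placebo. A shared rise would hide a real benefit in the paired test.

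Last, the gain from ANCOVA depends on r. An old clinical biopsy, perhaps taken before washout and perhaps read by another pathologist, may correlate weakly with week 12, and then the gain is 0 to 3 points. The 48% figure implies a week-12 SD of about 65, a value the plan does not give. This too stands, but at low r the adjustment costs almost nothing.

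**Conclusion.** The concern holds and should be fixed. No primary test of peak count is named, change is tested only inside the treated arm, the Study Summary keeps only that test for the count, and the between-arm analysis of change assumed in 7.1 is not planned. The planned between-arm week-12 test controls type I error under randomisation with complete data, so a sound analysis is available; it is neither designated nor adjusted.

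The size depends on two assumed quantities. For shared falls of 5 to 10 eos/hpf the paired test is falsely significant in 7% to 29% of trials. For r between 0.3 and 0.7 at SD of change 50, leaving out baseline costs 3 to 28 points of power (86 − 83 and 76 − 48). At r of 0.2 or less, or at SD 30 with r of 0.5, it costs about 1 point. All power figures are on the raw count scale.

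**What to change.** In 7.2, name one primary efficacy analysis: week-12 peak eosinophil count compared between arms by ANCOVA on arm and baseline peak count, two-sided 0.05, reported as an adjusted difference with 95% CI. Fix the scale in advance, for example log(count + 1), because counts may be skewed.

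Section 7.3 lists four populations without assigning one to this test. State that patients are analysed as randomised if they have an observed week-12 biopsy. Since "Data will be collected on withdrawn subjects up until the point of study withdrawal", also state a sensitivity analysis for missing biopsies.

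Use the same model for the DSQ, and for EREFS only if a baseline score exists, because no baseline EGD is scheduled. Label the treated-arm paired test descriptive and make the Study Summary match. If ANCOVA is not adopted, at minimum name the planned between-arm week-12 test as primary.

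The cost is wording in 7.2 and the Summary, one degree of freedom and one missing-biopsy rule. No visits or biopsies are added.
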